### *Differential treatment effects*

To determine whether effects of treatment on the primary endpoint depends on any of the baseline characteristics, we will test the interaction between the baseline characteristics and treatment effect in the regression model. If evidence of an interaction is observed using a threshold of  $p < 0.2$ , we will proceed to subgroup analyses. For categorical variables, endpoints will be compared between within categories. For continuous variables, we will display the partial effects plots showing how treatment effects change with the putative subgrouping variable.

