### *Descriptive Analysis*

To characterize the study sample, baseline demographic and clinical data will be described overall and by group. Categorical variables will be described using frequencies and proportions, and continuous variables will be described using means and standard deviations, as well as medians and interquartile ranges. Missingness will be reported for each variable. Graphical summaries using box plots, violin plots, and/or histograms may be used to describe the data graphically. At a minimum, the following variables will be described at time of enrollment:

- Age (years)
- Gender (male, female, unknown)
- Race (African American, Asian/Pacific Islander, Caucasian, Multiple, Native American, Other, Unknown)
- Ethnicity (Hispanic, Non-Hispanic, Unknown)
- Census tract area deprivation index

We will describe all of the outcome variables overall and grouped by study arm using the same approach as for the demographic data. Summary statistics and graphical representations may be displayed, and missingness will be reported for each variable.

No statistical comparisons between groups will be done for this descriptive analysis.

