### *Main Analysis*

The primary outcome variable (hospital index length of stay) will be compared between groups using an adjusted generalized linear model. Since the data are positive and may be skewed, like a gamma distribution, we may use a negative inverse link function, a proportional odds model, or transform the data.

In this analysis, group assignment is the main predictor variable. For drawing conclusions about the effect of the Bridge clinic, a critical p-value of 0.05 for the effect of treatment group assignment on the primary outcome will be used. The model will be adjusted for age, race, ethnicity, and area deprivation index. The influence of continuous variables will be assessed using restricted cubic splines with a minimum of three knots. We do not expect missingness in our primary outcome. If there are missing covariates, cases will not be excluded; we will use multiple imputation with predictive mean matching for missingness in adjusting covariates.

Secondary and implementation outcomes will be compared between study groups using adjusted generalized linear models, just as for the primary endpoint. Binary endpoints will use a logit link function. For counts, such as number of medication refills, either a zero-inflated Poisson or a negative binomial model will be fit.

Exploratory outcomes for OPAT patients will not be compared between study groups but will be reported by study group.

There may be missingness in secondary or implementation outcomes. If there are missing outcomes, these may be imputed if they occur in less than 5% of cases. Otherwise, the cohort for which the outcome is available will be described, along with the results of the model evaluating treatment effects in this cohort. All model results will be summarized with point estimates and 95% confidence intervals (CIs), which will be emphasized over p-values when reporting the results for secondary and implementation outcomes. No adjustments for multiplicity will be made.

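### Subgroup analysis opens on any treatment interaction with p < 0.2, without multiplicity control or an exploratory label; tested factor by factor, 59% to 67% of trials with no effect modification would trigger it

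*SAP*

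**What the plan says.** The SAP section Differential treatment effects concerns the primary endpoint, length of the index stay. It states that "we will test the interaction between the baseline characteristics and treatment effect in the regression model". The trigger for subgroup analyses is worded "If evidence of an interaction is observed using a threshold of" p < 0.2. The next step depends on the type of variable: "For categorical variables, endpoints will be compared between within categories", while a continuous variable gets a partial effects plot.

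The section neither lists the characteristics nor says whether there is one test per factor or one joint test. Two other places suggest a list:

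- Descriptive Analysis names five (age, gender, race, ethnicity, deprivation index), introduced by "At a minimum, the following variables will be described at time of enrollment".
- Main Analysis names four, without gender: "The model will be adjusted for age, race, ethnicity, and area deprivation index".

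Main Analysis also says "No adjustments for multiplicity will be made". Its preference for confidence intervals over p-values is stated for secondary and implementation outcomes only. Nothing in the subgroup section calls its results exploratory, or says that the interaction estimate is to be interpreted rather than the p-values inside each category.

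**The concern.** A cut-off of 0.2 applied to several factors will often be crossed by chance. The categorical factors that cross it are those in which chance has already separated the categories, so the comparisons then displayed have been selected for contrast. If the overall effect is real but each category has only moderate power, the natural result is a significant benefit in one category and none in the other, although the true effect is the same in both. Without an exploratory label or a rule on interpretation, that pattern can be read as a finding. At stake is the credibility of any statement about who benefits from the clinic. The answer to the main question is not at stake.

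**Working it through.** **Inputs.** Threshold 0.2 (SAP, Differential treatment effects). Four or five factors (SAP, Main Analysis or Descriptive Analysis). 336 patients, 168 per group (SAP, Sample Size Considerations). Log-scale mean ln(5.5), SD ln(2.7) = 0.993, reduction 1.5 days (Protocol 10.0, Interim Analysis). Reading the reduction as 5.5 to 4.0 days gives ln(5.5/4.0) = 0.318. Two-sided 0.05 is assumed, since the SAP does not state sidedness.

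**The plan's own figure.** The documents give no trigger rate, so the nearest figure to reproduce is the sample size: n per group = 2 × (1.960 + 0.842)² × (0.993/0.318)² = 153, not 168. At 168 per group the standard error is 0.993 × √(2/168) = 0.108, z = 0.318/0.108 = 2.94, and power is 83.6%. This gap does not affect the trigger rate.

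**How often the rule triggers with no effect modification** (independent tests):

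- five factors: 1 − 0.8⁵ = 67.2%
- four factors: 1 − 0.8⁴ = 59.0%
- the three categorical factors alone: 1 − 0.8³ = 48.8%
- one joint test: 20%
- for comparison, five tests at 0.05: 1 − 0.95⁵ = 22.6%

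**What a flagged factor shows.** Take two categories of 168 patients, 84 per arm in each, and a uniform effect of 0.318.

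- Standard error within a category: 0.993 × √(2/84) = 0.153.
- Power within a category: z = 0.318/0.153 = 2.08, so Φ(2.08 − 1.96) = 55%.
- Without selection, significance in exactly one category has probability 2 × 0.55 × 0.45 = 50%.
- To trigger, the two estimates must differ by at least 1.282 × 0.153 × √2 = 0.278. That is 87% of the whole design effect (0.278/0.318), when the true difference is zero.

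Conditional on triggering, the share of cases with significant benefit in one category only, by simulation, is:

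| True overall effect | Share |
|---|---|
| Design effect | about 90% |
| Half of it | about 66% |
| None | 17% |

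Unequal categories lower the share. With 80% overall power it is 74% for an 80/20 factor and 57% for a 95/5 factor.

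**Five factors together.** Trials of 336 patients were simulated, 3,000 per scenario, with separate tests and three-knot splines for age and deprivation index. Category sizes are assumptions: gender 55/45, race 80/13/7, ethnicity 95/5, with latent correlation 0 or 0.3. The trigger rate was 64% to 68%. The share showing a split was:

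| True overall effect | Of triggered trials | Of trials flagging a categorical factor | Of all trials |
|---|---|---|---|
| Design effect | 61–63% | 84–85% | 41–42% |
| Half of it | 42–43% | 59–61% | 28–29% |
| None | 14–16% | 20–22% | about 10% |

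About 27% to 29% of triggered trials flag only age or deprivation index and so show no split.

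**The case against.** The best defence is that interaction tests have low power, so a lenient threshold is a sensible screen, and that a trigger is not a claim. Main Analysis ties conclusions about the clinic to the treatment effect on the primary outcome at 0.05 and reports all models with estimates and 95% CIs. Nothing says that category p-values will support a subgroup claim. All of that is true, but nothing rules such a claim out either. Low power also argues against a gate: imprecise estimates that miss the cut-off disappear, and exaggerated ones that pass it are shown.

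Other parts of the defence stand:

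- Five factors is one reading. On the four-covariate reading gender is not tested, and a joint test would trigger in only 20%. The wording about variables, taken by type, fits separate tests better but does not settle it.
- For very unequal factors the small category's low power produces splits with or without the gate. For a 95/5 factor at 80% power the share is 73% ungated and 57% once triggered.
- The plural in "endpoints will be compared between within categories" stands in a garbled sentence in a section that opens on the primary endpoint. It is weak evidence that other endpoints would be opened.
- The seven race codes are descriptive and include Unknown. Even spread would give 336/7 = 48 per level, but the analysis coding is not stated.

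A reader might infer that a false one-group-only result is the likely outcome of any trial with a uniform effect. The figures do not support this: about 41% of all trials would show one at the design effect, and about 10% with no effect. Nor do the documents say that subgroup results would decide who is offered the clinic. Protocol 7.0 speaks only of expanding or refining services.

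**Conclusion.** The point holds in a conditional form, and the SAP should be changed. Following the rule as written, with factors tested one by one and no effect modification, subgroup analysis is triggered in about 59% (four factors) to 67% (five) of trials, and more often if further baseline variables are added. If the clinic works at about the design effect, a flagged categorical factor will then usually show significance in one category only: about 90% for two equal categories, and 61% to 63% across all triggered trials once the plotted factors are counted. These shares rest on the 5.5 to 4.0 day reading of the effect, log SD ln(2.7), 336 patients, and the assumed category sizes. They fall with a smaller effect, and with no effect a split is uncommon. This is more than missing detail, because the stated rule selects chance contrasts for display and exaggerates them. The primary conclusion is unaffected.

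**What to change.** Rewrite Differential treatment effects to:

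- name the factors, and say whether each is tested separately or all jointly;
- remove the p < 0.2 gate;
- report, for every named factor whatever its p-value, the interaction estimate with 95% CI on the primary endpoint only, labelled exploratory;
- show the partial effects plots for age and deprivation index in all cases;
- pool race levels too sparse to estimate, with the pooling rule set before unblinding;
- state that no subgroup claim will rest on category-specific p-values.

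The cost is SAP wording and a few more rows in the report. There is no added data collection and no change to the primary analysis. The SAP Introduction places the document before final data collection and unblinding, and at that stage the change is both cheap and credible.

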### **Summary**

The results of this study will help to determine whether the Bridge Clinic is effective at improving patient outcomes. The analysis approach we describe is selected based on the trial's pragmatic nature and the intent to understand the effectiveness of Bridge Clinic when compared to TAU.
